2.3.3 ASSESSMENT OF POTENTIAL RISKS AND BENEFITS

Although hypoglycemia has never been demonstrated with intranasal insulin at lower dose in humans, the potential for this safety concern exists in this study. Mechanisms of insulin transport into the brain through the olfactory epithelium is more efficient than vascular absorption of regular insulin into the systemic circulation, but Kullmann et al have demonstrated small but measurable increases in serum insulin with intranasal administration and have shown these to represent dose-dependent spillage (11).

There is insufficient data to show whether this dose response is linear, and the very small changes in insulin level detected did not manifest as a measurable change in glucose (11). Of note, a minority of the 19 studies in which participants received 160 U of intranasal insulin also reported clinically insignificant but measurable decreases in serum glucose ranging from 0.2 to 0.4 mmol/L. Based on these data, we have developed an initially conservative dose escalation study that has the potential to adapt the magnitude of dose escalation with accumulating data if lower dose tiers demonstrate the same overwhelming safety signals seen in the prior data. Point-of-care (POC) serum glucometry will be performed at 0, 15, 30, 60, 120, 180, and 240 minutes after each intranasal insulin administration. Hypoglycemia as defined by a blood glucose of <45mg/dL will be treated with 50 ml of intravenous D50W and food. The subject will also be monitored until achieving two consecutive measurements of blood glucose > 70mg/dL, measured at 30 minutes apart. If blood glucose falls to ≤70 mg/dL but not <45 mg/dL, the blood glucose will be monitored every 30 minutes until it returns to >70 mg/dL.

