3 OBJECTIVES AND ENDPOINTS

OBJECTIVES	ENDPOINTS	JUSTIFICATION FOR ENDPOINTS
Primary		
Determine the maximum tolerated dose of intranasal insulin in healthy participants	Primary endpoint: The primary safety outcome will be severe hypoglycemia as defined by blood glucose <45mg/dL at any post administration glucose check during a study visit.	The American Diabetes Association defined severe hypoglycemia as “severe cognitive impairment requiring external assistance for recovery” without assigning a blood glucose cutoff (12). As such, we chose blood glucose < 45mg/dL as the cutoff for severe hypoglycemia based on prior clinical studies (13).
Secondary		
Characterize the pharmacokinetics and pharmacodynamics (PK-PD) of intranasal insulin in healthy participants	Secondary endpoints will include the change in blood glucose, insulin, and C-peptide levels for up to 4 hours after drug administration to evaluate for any systemic absorption of intranasal insulin.	Prior studies have not characterized the PK-PD of conventional insulin formulation doses above 160 U administered intranasally.

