9 STATISTICAL CONSIDERATIONS

9.1 STATISTICAL HYPOTHESES

- Primary Efficacy Endpoint(s): Severe hypoglycemia (DLT) as defined by blood glucose <45mg/dL.

The maximum dose that is under the threshold of a 0.9 probability of having a DLT proportion of greater than 0.1 will be considered the maximum tolerated dose for this study.

- Secondary Efficacy Endpoint(s): Change in blood glucose, insulin, and C-peptide levels for up to 4 hours after drug administration to evaluate for any systemic absorption of intranasal insulin.

Our main secondary hypothesis is the secondary efficacy endpoints are not associated with increasing doses of insulin. For example, change in blood glucose from baseline to 4 hours will be similar in the placebo and highest doses.

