9.4.3 ANALYSIS OF THE SECONDARY ENDPOINT(S)

First, we will graphically plot the relationship between the secondary endpoint and dose. We will explore these plots to determine a reasonable functional form (i.e. linear, Emax, log transformed, log-logistic) for dose-response. We will consider dose as a linear predictor in addition to the most reasonable functional form. However, we will not fit other models if the linear predictor is reasonable.

We will fit generalized linear models to predict change in glucose from baseline given dose. We will use a random effects model (with a random intercept for each subject). The main predictor variable will be dose. The main covariate will be the baseline value for the covariate for variables that are measured longitudinally (i.e. model predicts 4 hour glucose, and baseline glucose is a covariate in the model).

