9.4.4 SAFETY ANALYSES

Secondary analyses include modeling of dose-safety curves based on primary and secondary safety outcomes, and modeling of pharmacokinetics/pharmacodynamics based on dose and serial serum insulin measurements if there is sufficient signal. Analyses of the effects of intranasal insulin on indicators of glycemic variability will also be explored.

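### The main secondary hypothesis is that there is no dose effect, but the plan sets no margin or interval by which a non-significant result could support it

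*Combined protocol and SAP*

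**What the plan says.** Section 9.1 gives the secondary endpoints as "Change in blood glucose, insulin, and C-peptide levels for up to 4 hours after drug administration to evaluate for any systemic absorption of intranasal insulin". It then states the hypothesis: "Our main secondary hypothesis is the secondary efficacy endpoints are not associated with increasing doses of insulin". Its example is that "change in blood glucose from baseline to 4 hours will be similar in the placebo and highest doses".

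Section 3 words the secondary objective differently, as an estimation aim: "Characterize the pharmacokinetics and pharmacodynamics (PK-PD) of intranasal insulin in healthy participants".

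On analysis, section 9.4.3 says "We will fit generalized linear models to predict change in glucose from baseline given dose", with a random intercept per subject and dose as the main predictor. Only glucose is written out. On the shape of the dose-response it says "We will explore these plots to determine a reasonable functional form". Section 9.4.4 adds "modeling of pharmacokinetics/pharmacodynamics based on dose and serial serum insulin measurements if there is sufficient signal".

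95% confidence intervals are specified for event rates (9.4.2) and baseline summaries (9.4.5), but not for a dose slope or a dose contrast. The sample-size section (9.2) deals with the DLT rule alone. The only effect size for glucose is in section 2.3.3, where a minority of the studies at 160 U reported "clinically insignificant but measurable decreases in serum glucose ranging from 0.2 to 0.4 mmol/L".

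**The concern.** The hypothesis is a statement of absence, while the model looks for presence. A non-significant dose effect agrees with the hypothesis whether the true effect is nil or the data are too noisy to show it. With no margin and no required interval, nothing in the plan separates the two cases, and imprecision works in favour of the stated hypothesis.

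At stake is the secondary conclusion on systemic absorption at doses up to 1000 U. Section 3 says that conventional insulin formulations have not been characterised intranasally above 160 U. Glucose falls were reported in some of the 160 U studies, so the size of effect that this trial can exclude is what a reader will want to know.

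**Working it through.** **The plan's own figure.** The only operating characteristics in the plan are those for the DLT rule in 9.2. With a Beta(0.2, 0.8) prior, looks at 6, 12, 18 and 24 participants, and a dose dropped when Prob(θ > 0.1) ≥ 0.9, the cut-offs are 2, 3, 4 and 5 DLTs. An exact binomial recursion at a true rate of 0.1 gives 0.1898 for early stopping and 0.2062 for declaring the dose toxic, as in scenario 5. All nine scenarios reproduce. So 24 participants is supported for the DLT rule. There is no corresponding figure for the secondary endpoints.

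**Inputs for the secondary endpoint**
- 24 participants with 6 administrations each (4.1), so 144 observations if complete.
- No-DLT dose schedules (6.1.2): 0, 200, 400, 600, 800, 1000 U in cohort 1; 0, 400, 600, 800, 900, 1000 U in cohort 2; 0, 600, 700, 800, 900, 1000 U in cohorts 3 and 4.
- Effect of interest: 0.4 mmol/L × 18 = 7.2 mg/dL, the upper end of the range in 2.3.3, used as a reference size only.
- Assumed: an SD of the within-person difference in glucose change of 10, 15, 20 or 25 mg/dL, and a two-sided 5% level. The documents give neither.

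**Planned model, linear slope**
- Within-subject sum of squares of dose, in units of 1000 U: 0.700 for cohort 1, 0.688 for cohort 2, 0.633 for cohorts 3 and 4.
- Total = 6 × 0.7000 + 6 × 0.6883 + 12 × 0.6333 = 15.93.
- Residual SD = SD of difference / √2. SE of the effect over 1000 U = residual SD / √15.93. Degrees of freedom = 144 − 24 − 1 = 119, t = 1.980.
- At SD 20: residual SD 14.14, SE 3.54, half-width 1.980 × 3.54 = 7.0 mg/dL.

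**Paired 1000 U versus 0 U, as in the example in 9.1**
- SE = SD / √24, 23 degrees of freedom, t = 2.069.
- At SD 20: SE 4.08, half-width 2.069 × 4.08 = 8.4 mg/dL.

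Miss probabilities come from the noncentral t distribution with noncentrality 7.2 / SE.

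| Assumed SD of difference (mg/dL) | Slope: 95% CI half-width | Slope: chance of missing 7.2 | Paired: 95% CI half-width | Paired: chance of missing 7.2 |
|---|---|---|---|---|
| 10 | 3.5 | 2% | 4.2 | 8% |
| 15 | 5.3 | 23% | 6.3 | 38% |
| 20 | 7.0 | 48% | 8.4 | 61% |
| 25 | 8.8 | 64% | 10.6 | 73% |

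If only 12 participants reached 1000 U, the paired half-width at SD 20 would be 12.7 mg/dL.

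**What a similarity claim would require.** Suppose the true difference is zero and similarity is claimed only when the paired 95% CI lies wholly within ±7.2 mg/dL. With 24 participants the claim would succeed about 84% of the time at SD 10, 61% at SD 12 and 25% at SD 15.

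**The case against.** The strongest reply is that section 9.1 states an expectation and not a decision rule. It sets no test, level or criterion, and no sentence says that a non-significant slope will be reported as absence of systemic absorption. That is correct. A reader might infer such a report from the hypothesis and from the purpose given for the endpoints, but it remains an inference.

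A second reply is that the model in 9.4.3 is adequate. This also stands. A random-intercept dose model yields an estimate and can yield an interval, so it would be wrong to say that it can only fail to find an association. The gap lies in the hypothesis and in what is to be reported.

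A third reply is that the paired comparison understates the planned analysis, which uses all doses. It does, if the response is linear, and the table therefore shows the slope first. The paired figures remain relevant because the example in 9.1 is that contrast.

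A fourth is that the protocol's evidence is mixed, so predicting no association is not perverse. Section 2.3.3 reports dose-dependent spillage into serum and small glucose falls, but also says that the insulin changes produced no measurable glucose change. Section 4.2 cites blood insulin that did not differ from placebo at 40 IU. This is fair, and the point does not depend on the hypothesis being improbable.

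None of these replies supplies a margin or an interval.

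**Conclusion.** The point holds as one of wording and reporting. The main secondary hypothesis asks for a conclusion of no association, and a non-significant dose effect could not support it without a bound on the effect. How much this matters depends on an SD that the documents do not give. At 10 mg/dL the trial would be informative about a 7.2 mg/dL fall. At 20 mg/dL or more, it would miss such a fall about half the time or more often. The figures assume complete data, a linear response for the slope, 1000 U retained throughout and a two-sided 5% level. They concern glucose only.

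Two stronger readings are not supported. First, a reader might infer that a null slope would enter the safety margin for lay administration. Sections 2.1 and 4.3 tie that margin to the MTD, and sections 9.1 and 9.4.1 set the MTD from the DLT posterior alone. The consequence is therefore limited to the secondary PK-PD conclusion. Second, a reader might take 0.4 mmol/L as the limit of clinical insignificance. Section 2.3.3 reports an observed range and does not say that larger falls would matter, so it is not an equivalence limit.

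**What to change.** In 9.1, replace the no-association hypothesis with an estimation aim that matches the secondary objective in section 3. In 9.4.3, state that for glucose, insulin and C-peptide the report will give the dose slope and the difference between the highest retained dose and 0 U, each with a 95% CI. Add that a non-significant dose effect will not be reported as similarity or as absence of systemic absorption, and that the largest effect not excluded by the interval will be stated.

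If the sponsor wishes to claim similarity, it should fix and justify a margin before seeing the data. The range in 2.3.3 can serve as a reference for that justification but cannot replace it.

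The cost is SAP wording, with no added participants, samples or change of model. The downside is that the secondary conclusion may be less favourable. With a margin as tight as ±7.2 mg/dL, a similarity claim would often fail at moderate SDs even if there were no true difference. Pure estimation avoids that problem.

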9.2 SAMPLE SIZE DETERMINATION

Overall, for any dose we estimated whether the study would end, with different assumptions of the probability of toxicity for a given dose. These ranged from 0.01 to 0.25. It is possible, however, that a dose tier may not be desirable despite having not been dropped. For example, there will be about an 82% probability that the toxicity rate is > 0.1 if 4 out of 24 participants experience a DLT, then the point estimate using the Bayesian model will be that arm has a 0.17 probability of DLT (slightly above the raw observed rate of 0.125 due to the Bayesian prior).

The design has approximately 80% “power” at the margin (scenario 5). That is, if the true rate of DLT is 0.1 at a dose, the DLT will NOT be declared toxic using the pre-specified definition ($\text{Prob}(\theta > 0.1) \geq 0.9$) just under 80% of the time.

It is important to note that the table below is for a single dose with 24 observations. As the trial progresses, we will generate independent estimates of the probabilities for each dose. The average number of patients indicates that the dose will stop early some proportion of the time. The average number of toxicities provides the average number of DLTs observed within a simulated trial when the true probability of toxicity is given (for example 0.1 in scenario 5).

Table: Operating Characteristics for a Dose Assuming N of 24

Scenario	Prob.Of.Tox	Prob Early.Stop	ProbDeclare.Tox	Avg.N.Patients	Avg.N.Tox	Obs.Tox.Rate
1	0.01	0.0016	0.0016	23.9724	0.2397	0.0104
2	0.025	0.0105	0.0105	23.8235	0.5956	0.0272
3	0.05	0.0453	0.0467	23.2792	1.164	0.0583
4	0.075	0.1062	0.1125	22.3836	1.6788	0.0921
5	0.1	0.1898	0.2062	21.1965	2.1196	0.127
6	0.125	0.2892	0.3196	19.8036	2.4754	0.1617
7	0.15	0.3962	0.4415	18.2978	2.7447	0.1952
8	0.2	0.6031	0.669	15.277	3.0554	0.2563
9	0.25	0.7684	0.8336	12.6203	3.1551	0.3089

9.3 POPULATIONS FOR ANALYSES

Male or female volunteers at least 18 years of age and older, who meet study inclusion and exclusion criteria.

9.4 STATISTICAL ANALYSES

9.4.1 GENERAL APPROACH

For each dose DLT probability θ , we will calculate the $\text{Prob}(\theta > 0.1)$. The maximum dose that is under the threshold of a 0.9 probability of having a DLT proportion of greater than 0.1 will be considered the maximum tolerated dose for this study.

We will also report the observed toxicity rate for each dose. Depending on the number of DLT observed, we may fit a dose response model that uses data from all doses to fit a dose-toxicity curve. We also will plan to use dose response models for the analyses of the secondary endpoints.

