6.1.2 DOSING AND ADMINISTRATION

Rules for assigning patients

Within subject rules (subject progressing through tiers for cohort):

1. If a volunteer experiences severe hypoglycemia (blood glucose <45 mg/dL), they will be assigned a dose 100 U less for the next round and for all subsequent rounds.
2. If a volunteer experiences severe hypoglycemia a second time, they will be withdrawn from the study.

Study wide rules (determine which dose tiers are allowable for all future volunteers):

1. All doses from 0 to 1000 U by increments of 100 U will be eligible for testing in the study.
2. If there is greater than 0.9 probability that a dose has a greater than 0.1 toxicity rate, that dose will be removed for all future cohorts (see below).

Allocation Rules

Initial Allocation and Strategy:

Overall, the philosophy of allocation is to assign as many patients as possible to higher doses, while also limiting exposure to toxic doses. The trial will start the first cohort with 200, 400, 600, 800, and 1000 U.

Allocation Adjustment Rules:

After each hypoglycemic event, we will recalculate the toxicity probabilities for that dose to see if a dose removal threshold has been met.

If a dose meets the criteria for removal, that dose and all higher doses will be removed from future participants and cohorts. For the next cohort or patient within a cohort, the highest additional doses available will be used. For example, if 700 U was removed, then 200, 300, 400, 500, 600 U would be the new future allocation.

If a cohort completes with no observed episodes of dose-limiting toxicity (DLT), the smallest (and any smaller) doses will drop, and the highest unused dose will replace it. For example, after zero episodes of DLT in Cohort 1 at any dose, Cohort 2 will use 400, 600, 800, 900, and 1000 U. Doses 100 and 200 U will be dropped.

If a cohort has any DLT, but no dose is dropped (only 1 DLT in two different doses for example), the initial allocation rules will be used for the next cohort (200, 400, 600, 800, 1000 U).

4 Cohort Example - No DLT (Demonstrated by Schema Figure 1.2.2)

Cohort 1: Participants #1 to 6

The doses will be 0, 200, 400, 600, 800, and 1000 U.

Cohort 2: Participants #7 to 12

If there were 0 events in Cohort 1, then the doses for Cohort 2 will be 0, 400, 600, 800, 900, and 1000 U. 200 U will be dropped and 900 U will be entered.

Cohort 3: Participants #13 to 18

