If there were 0 events in Cohorts 1 and 2, then the doses for Cohort 3 will be 0, 600, 700, 800, 900, and 1000 U. 400 U will be dropped and 700 U will be entered.

Cohort 4: Participants #19 to 24

Same as Cohort 3.

Other situations (more than one DLT)

Please also refer below to rules for discontinuing a dose.

If a dose (or doses) is dropped during or after a cohort, the highest available unused doses will be used for the next patients within that cohort and the next cohort. For example, if 1000 U is dropped, the future doses will be 200, 400, 600, 800 and 900 U. Or, if 800 U and all higher doses are dropped, then 200, 400, 500, 600, and 700 U will be the next set.

As one example, if there is 1 DLT in a different dose in each of the 4 cohorts, the trial will simply allocate using the initial rules for all cohorts, with the exception of the within subject adjustment rule noted above.

For example, if there are no DLTs in Cohort 1, then Cohort 2 will use 400, 600, 800, 900, and 1000 U. If Cohort 2 also has no DLTs, then 300 and 400 U will drop and Cohort 3 will use 600, 700, 800, 900, and

1000 U. Even if there are no DLTs in Cohort 3 given that allocation, we will continue that allocation as it utilizes the 5 highest available doses.

If higher doses are dropped, they cannot be reconsidered in the study.

If lower doses are dropped, they can re-enter the study. This would occur if higher doses needed to be dropped by having DLTs over the threshold. The lower doses may need to re-enter in order for each subject to have 5 potential doses.

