7 STUDY INTERVENTION DISCONTINUATION AND PARTICIPANT DISCONTINUATION/WITHDRAWAL

7.1 DISCONTINUATION OF STUDY INTERVENTION

The rules for stopping or changing an individual dosing regimen are given above in the Dosing and Administration section.

Rules for discontinuing a dose

We are interested in proceeding with a dose if we remain confident that the Dose Limiting Toxicity (blood glucose < 45 mg/dL) is < 0.1 (1 in 10).

Using the Bayesian Toxicity Monitoring software from MD Anderson (<https://ibl.mdanderson.org/BTM/>)

We define Toxicity parameters as:

Probability of DLT is represented by θ

Maximum probability of DLT allowed (θ_{\max}): 0.1

When calculating the probability of DLT at a dose, we will use a Beta(0.2,0.8) prior. This is a vague prior with a median of 0.2 and a 95% credible interval from 0 to 0.94. There is greater density over probabilities of DLT near zero in this non-symmetric distribution. Each DLT is added to the A parameter of the beta distribution, and each patient who is DLT free is added to the B parameter of the B distribution. Therefore, with the prior included, if 24 participants have DLT on a dose, the probability of DLT can be described with a Beta(0.2,24.8) distribution. In this setting, the posterior estimate for DLT probability is 0.008 (or 0.8%). In addition, the probability that that dose has a DLT proportion over 0.1 is only 0.006 (or 0.6%).

$\text{Prob}(\theta > \theta_{\max}) \geq 0.9$ (Or that there is 90% or greater probability that the DLT is greater than 0.1)

We define the probability that $\text{Prob}(\theta > \theta_{\max})$ as the final output of the trial for each dose. For each dose, we will also calculate the probability that toxicity is greater than 0.1 at that dose.

The below table (SB1A) illustrates the probability that DLT is greater than 0.1 based on the number of observed events.

Table SB1A: Probability of Early Stopping
Number of Toxicities
(Highlighted = Prob(e > 0.1) >= 0.9)

	0	1	2	3	4	5	6	7	8	9	10	11	12	13	14	15	16	17	18	19	20	21	22	23	24
Number of Patients																									
6	.0884	.6292	.9196	.9990	.9993	1.0000	1.0000	NA	NA	NA	NA	NA	NA	NA	NA	NA	NA	NA	NA	NA	NA	NA	NA	NA	NA
12	.0333	.3613	.7196	.9151	.9816	.9971	.9997	1.0000	1.0000	1.0000	1.0000	1.0000	1.0000	NA	NA	NA	NA	NA	NA	NA	NA	NA	NA	NA	NA
18	.0141	.2027	.5135	.7773	.9220	.9786	.9954	.9992	.9999	1.0000	1.0000	1.0000	1.0000	1.0000	1.0000	1.0000	1.0000	1.0000	1.0000	1.0000	NA	NA	NA	NA	NA

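### The MTD rule judges each dose on its own posterior and ignores the closure of doses above a removed one, so as written it can name a dose the trial has already removed

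*Combined protocol and SAP*

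**What the plan says.** Two rules use the same posterior probability.

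- **Removal (Section 6.1.2).** The trigger is "greater than 0.9 probability that a dose has a greater than 0.1 toxicity rate, that dose will be removed". Removal is ordered: "If a dose meets the criteria for removal, that dose and all higher doses will be removed from future participants and cohorts". Closure is permanent: "If higher doses are dropped, they cannot be reconsidered in the study".
- **MTD (Sections 9.1 and 9.4.1, same wording).** "The maximum dose that is under the threshold of a 0.9 probability of having a DLT proportion of greater than 0.1 will be considered the" MTD. Neither statement refers to the removal rule, limits the candidates to open doses, or requires the lower doses to pass.

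The posteriors share no information across doses. Section 7.1 says "When calculating the probability of DLT at a dose, we will use a Beta(0.2,0.8) prior", and Section 9.2 says "As the trial progresses, we will generate independent estimates of the probabilities for each dose". Section 7.1 also makes the per-dose probability the final output of the trial, with no exception for closed doses. The dose-response model in 9.4.1 is optional and is not tied to the MTD.

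**The concern.** Removal assumes that if a dose is too toxic, every higher dose is too. The MTD rule drops that assumption. When the removed dose is not the top one, the doses above it are closed without having failed on their own data, and the MTD rule still sees them as candidates.

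The design makes such doses look clean. After a DLT, Section 6.1.2 steps the participant down by 100 U, so those who reacted at a lower dose do not contribute data at the higher ones. Closure then stops further exposure there.

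Determining the MTD is the only primary objective (Section 3). Sections 2.1 and 4.3 use it to guide dose-finding in cardiac arrest and to estimate the safety margin for use by bystanders. The unrestricted rule chooses from a larger set of doses than one limited to open doses. It can therefore only give the same MTD or a higher one, never a lower one.

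**Working it through.** **Inputs.** Beta(0.2, 0.8) prior, DLT limit 0.1 and removal threshold 0.9 (Section 7.1); starting doses 200, 400, 600, 800 and 1000 U (6.1.2); removal at 2 DLTs in Cohort 1, then 3, 4 and 5 in total through Cohorts 2, 3 and 4 (7.1).

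**Formula.** With k DLTs in n participants at a dose, Prob(θ > 0.1) = 1 − F(0.1), where F is the distribution function of Beta(0.2 + k, 0.8 + n − k).

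**Step 1: reproduce the plan's figures.** The formula gives 2/6 = 0.9196, 3/12 = 0.9151, 4/18 = 0.9220 and 5/24 = 0.9310, as in Table SB1A. Of the entries checked, only 3/6 differs (printed .9990, computed 0.9900), which does not matter here. With looks at 6, 12, 18 and 24 participants and boundaries 2, 3, 4 and 5, all nine rows of the operating-characteristics table in 9.2 reproduce. For scenario 5, the probability of declaring toxicity is 0.2062, so 1 − 0.2062 = 0.7938 is the roughly 80% the plan quotes.

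**Step 2: a record where the rules collide.**

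1. Cohort 1 has one DLT at 600 U. 1/6 gives 0.6292, so nothing is removed. The other five take 800 U and 1000 U without a DLT.
2. Because Cohort 1 had a DLT but lost no dose, 6.1.2 gives Cohort 2 the starting doses again.
3. Cohort 2, moving visit by visit, has two DLTs at 600 U. The total is 3/12, Beta(3.2, 9.8), Prob = 0.9151. All doses from 600 U up are closed before this cohort reaches 800 U.
4. 1000 U stays at 0/5, Beta(0.2, 5.8), Prob = 0.1065, which is below 0.9.
5. Sections 9.1 and 9.4.1 therefore name 1000 U, which is closed and lies 1000 − 600 = 400 U above a dose judged too toxic.

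**Step 3: a second record, within Cohort 1.** Suppose participants are staggered, so that four have already taken 1000 U without a DLT when the second DLT at 800 U occurs. 800 U is then 2/6 = 0.9196, and 800, 900 and 1000 U are closed. 1000 U at 0/4 gives 0.1297, and the rule again names it. Restricted to doses below 800 U, the highest candidate is 700 U, the step-down dose, at 0/2 = 0.2043.

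**Step 4: how easily a closed dose passes.**

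| Data at the closed dose | Prob(θ > 0.1) |
|---|---|
| never given (prior only) | 0.4077 |
| 0/4 | 0.1297 |
| 1/4 | 0.7492 |
| 0/6 | 0.0884 |
| 0/10 | 0.0453 |
| 2/10 | 0.7909 |

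All are below 0.9. The 0/6 row would also pass a much stricter cut-off and a minimum of six exposures, so neither of those changes would cure the problem.

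**Step 5: how often.** The simulation ran four cohorts of six, moving visit by visit, with 4,000 trials per curve. DLTs were independent across visits. Removal needed at least 2 DLTs and Prob ≥ 0.9, step-down administrations were not counted, and the trial stopped if 500 U or lower was removed. Only doses given to at least one participant were candidates. The linear rises to 0.05 or less come from a separate run of 3,000 trials per curve on the same assumptions.

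| Assumed true DLT rates | Trials naming a dose above a removed one |
|---|---|
| linear to 0.01 / 0.025 / 0.05 at 1000 U | about 0.2% / 0.8% / 3.6% |
| linear to 0.10 | 9% |
| linear to 0.20 | 29% |
| linear to 0.30 | 42% |
| two steeper logistic curves | 23–29% |
| flat 0.05 to 0.10 | 6–25% |

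Leaving out the rises to 0.05 or less, requiring at least six exposures at the named dose leaves 4–25%.

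Other readings of the conduct rules (participants in sequence or in parallel; removal by the cohort table or after each event) give 10–28%, 35–61% and 46–84% for the linear rises to 0.10, 0.20 and 0.30, again for tested doses only.

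For the rise to 0.20, the median MTD is 1000 U under the rule as written and 700 U when restricted, with untested doses allowed. With tested doses only it is 900 U against 600 U.

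**The case against.** The strongest reply is that the plan, read as a whole, already excludes closed doses. Section 6.1.2 says "If higher doses are dropped, they cannot be reconsidered in the study", and the MTD is defined for this study. Section 9.2 remarks that a tier may be undesirable even if it was not dropped, which suggests that not being dropped is taken for granted. Section 9.4.2 makes the primary analysis descriptive, so readers would see the DLTs at the lower dose. That reading may well be what the authors intend. But the sentence stands among the allocation rules, next to the one on lower doses re-entering, and neither MTD statement cites it. The remark in 9.2 sets no eligibility condition. A pre-specified primary rule should not depend on the analyst overriding it.

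Some limits on the size do stand:

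- Under the flat curves and the linear rise to 0.10, no true rate exceeds the 0.1 limit. Removal is then a false alarm, and the higher dose named is within the limit. Only the steeper curves show a truly unsafe MTD.
- At very low true rates the problem is rare.
- The percentages depend on the stated simulation rules, some of which the plan leaves open.
- The 1000 U against 700 U contrast includes untested doses. The tested-only contrast, 900 U against 600 U, is the cleaner one.
- Dosing within this trial is unaffected, because closure already governs who receives what.

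**Conclusion.** The concern holds. As written, Sections 9.1 and 9.4.1 can declare as MTD a dose that 6.1.2 has permanently closed. The worked records prove this from the plan's own prior, limit and boundaries, with no assumed toxicity curve.

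The frequency does rest on assumed curves and on a reading of the allocation rules. Counting tested doses only, it is about 9–42% for linear rises to 0.10–0.30 under the Step 5 assumptions, higher under other readings, and below 4% for rises to 0.05 or less. Where true rates exceed 0.1 at the upper doses, the effect is to overstate the tolerated dose and the safety margin. This should be corrected before the MTD is derived, because it concerns the primary objective. Nothing here says which dose is the right MTD.

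**What to change.** Add an eligibility condition to the MTD statement in both 9.1 and 9.4.1, for example:

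> The MTD is the highest dose that is under the threshold and lies below every dose removed under 6.1.2 and 7.1. Doses closed because a lower dose was removed are not eligible. If no dose qualifies, no MTD is declared.

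State as well whether a dose that was never given can qualify, since it passes on the prior alone (0.4077). Continue to report posteriors for closed doses, labelled as closed.

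If no dose is removed, the eligibility condition changes nothing. It needs no extra participants, visits or data, and it alters no dosing, rescue or stopping rule. The one cost is that the declared MTD can be lower than under the present wording, including when a removal was a false alarm. The removal rule already accepts that cost.
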